**Table 7.2.2 Dose Modifications for Acalabrutinib with concomitant CYP3A inhibitors or inducers**

CYP3A*	Co-administered Drug	Acalabrutinib Dose Modification
Inhibition	Strong CYP3A inhibitor	Avoid concomitant use. If these inhibitors will be used short-term (such as anti-infectives for up to 7 days), interrupt acalabrutinib.
	Moderate CYP3A inhibitor	100 mg QD
Induction	Strong CYP3A inducer	Avoid concomitant use. If these inducers cannot be avoided, increase acalabrutinib dose to 200 mg BID.

\*Refer to [Section 5.9](#) for examples of CYP3A inhibitor and inducers

## 8.0 AGENT INFORMATION

### 8.1 Acalabrutinib (Calquence®, ACP-196)

Acalabrutinib has been FDA approved for adult patients with CLL or SLL or mantle cell lymphoma (MCL) with have received at least one prior therapy.

#### 8.1.1 Description

Structural Formula	
Molecular Formula	C 26 H 23 N 7 O 2
Molecular Weight	465.51 kDa

Acalabrutinib is a white to yellow powder with pH-dependent solubility. It is freely soluble in water at pH values below 3 and practically insoluble at pH > 6. Acalabrutinib supplied as yellow and blue hard capsules for oral administration, where each capsule contains 100 mg acalabrutinib and the following inactive ingredients: silicified microcrystalline cellulose, partially pregelatinized starch, magnesium stearate, and sodium starch glycolate. The capsule shell contains gelatin, titanium dioxide, yellow iron oxide, FD&C Blue 2 and is imprinted with edible black ink stating "ACA 100 mg".

#### 8.1.2 Mechanism of action

Acalabrutinib is a small-molecule inhibitor of BTK. Acalabrutinib and its active metabolite, ACP-5862, form a covalent bond with a cysteine residue in the BTK active site, leading to inhibition of BTK enzymatic activity. BTK is a signaling molecule of the B cell antigen receptor (BCR) and cytokine receptor pathways. In B cells, BTK signaling results in activation of pathways necessary for B-cell proliferation, trafficking, chemotaxis, and adhesion. In nonclinical studies, acalabrutinib inhibited BTK-mediated activation of downstream signaling proteins CD86 and CD69 and inhibited malignant B-cell proliferation and tumor growth in mouse xenograft models.

#### 8.1.3 Pharmacokinetics and Metabolism

Half-life:	1 hr acalabrutinib, 3.5 h ACP-5862
Distribution:	Highly bound to plasma protein
Metabolism:	Predominantly metabolized by CYP3A enzymes; ACP-5862 is a major metabolite
Excretion:	84% feces, 12% urine

#### 8.1.4 Toxicology

See [Section 6.1](#) for detailed list of anticipated AEs.

#### 8.1.5 Storage

Store at 20°C-25°C (68°F-77°F). Excursions are permitted to 15°C-30°C (59°F-86°F).

#### 8.1.6 Handling

National Institute for Occupational Safety and Health (NIOSH) recommends the use of single gloves by anyone handling intact tablets or capsules or administering from a unit-dose package. Use caution when handling acalabrutinib, avoid eye or skin contact with the drug product. If there is exposure to the drug product, the individual should be treated for physical exposure (skin washing) or inhalation (move to fresh air, as necessary), and, if needed, seek medical advice.

#### 8.1.7 Administration

See [Section 5.4](#)

#### 8.1.8 Supplier

Acalabrutinib will be supplied by the manufacturer, Astra Zeneca, and prepared by the local site pharmacy per manufacturer instructions. Following submission and approval of the required regulatory documents, a supply of acalabrutinib may be ordered from Astra Zeneca by completing a Drug Request Form.

#### 8.1.9 Accountability

The Investigator, or a responsible party designated by the Investigator, must maintain a careful record of the inventory and disposition of the study agent. (See the [NCI Investigator's Handbook for Procedures for Drug Accountability and Storage](#)).

Responsibility for drug accountability at the study site rests with the Investigator; however, the Investigator may assign some of the drug accountability duties to an appropriate pharmacist or designee. Inventory and accountability records must be maintained and readily available for inspection by the study monitor and are open to inspection at any time by any applicable regulatory authorities or other oversight bodies.

The Investigator or designee will collect and retain all used, unused, and partially used containers of study medication until full accounting has been completed. The Investigator or designee must maintain records that document:

- Investigational product delivery to the study site.
- The inventory at the site.
- Use by each participant including pill/unit counts from each supply dispensed.
- Return of investigational product to the Investigator or designee.
- Destruction or return of investigational product for final disposal.

These records should include dates, quantities, batch/serial numbers (if available), and the unique code numbers (if available) assigned to the investigational product and study participants.

The investigational product must be used only in accordance with the protocol. The Investigator will also maintain records adequately documenting that the participants were provided the correct study medication specified.

Completed accountability records will be archived by the site. At the completion of the study, the Investigator or designee will oversee shipment of any remaining study drug back to Astra Zeneca for destruction according to institutional standard operating procedures. If local procedures mandate site destruction of investigational supply, prior written approval must be obtained from Astra Zeneca.

#### 8.1.10 Destruction and Return

At the end of the study, or earlier upon approval from study management, unused supplies of study drug should be destroyed according to institutional policies. Drug supplies will be counted and reconciled in full at the site with all monitoring procedures complete before destruction. Destruction will be documented in the Drug Accountability Record Form.

### 9.0 CORRELATIVE/ SPECIAL STUDIES

---

The exploratory objectives of this study are to evaluate the T-cell repertoire in participants with AIHA-associated CLL that receive acalabrutinib. The effects of acalabrutinib treatment on T-cell repertoire will be evaluated by flow cytometry. Plasma cytokine level will be measured by relevant methods (for example, ELISA Research Sample Collection and Dispensation

#### 9.1.1 Correlative blood

##### 9.1.1.1 *Overview and Time points*

Peripheral blood will be collected prior to study treatment/procedures at the time points indicated in Table 9.1.2.1

**Table 9.1.2.1 Overview of correlative blood studies**

Time points of collection	Total volume collected	Tube type	Receiving laboratory	Type of analysis
C1D1, C4D1, C7D1, C13D1	15-20 ml	Green-top (sodium or lithium heparin)	Investigator Laboratory	FACS/Cytokine

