### 3.2 Exclusion Criteria

#### Prior and concomitant therapies

- \_\_\_ 1. therapeutic anticancer antibodies within 2 weeks;
- \_\_\_ 2. radio- or toxin-immunoconjugates within 10 weeks;
- \_\_\_ 3. BH3-mimetic venetoclax, PI3K inhibitors and other “targeted” therapy– within 6 half-lives;
- \_\_\_ 4. Ibrutinib, acalabrutinib or another BTK inhibitor within 12 months
- \_\_\_ 5. Patients on stable chronic AIHA treatments are allowed provided the dose has not changed in the 4 weeks prior to enrollment
- \_\_\_ 6. Allogeneic stem cell transplant within 1 year prior to Day 1 of protocol therapy, or ongoing immunosuppressive therapy for cGVHD
- \_\_\_ 7. Chemotherapy, radiation therapy, biological therapy, immunotherapy within 21 days prior to Day 1 of protocol therapy

\_\_8. Strong CYP3A4 inducers/ inhibitors. If the patient requires a strong CYP3A inhibitor/inducer, they should not be enrolled even if it could be held for 14 days before the first dose of study drug.

\_\_9. Proton pump inhibitors (but patients who switch to H2-receptor antagonists or antacids are eligible for enrollment).

\_\_10. Chronic use of corticosteroids (>2 weeks) in excess of prednisone 60 mg/day or its equivalent within 4 weeks prior to start of study therapy. Rescue steroids are allowed during trial.

\_\_11. Vitamin K antagonists

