#### 5.2 Cycle Definition

The treatment cycle will be 28 days. Cycle 1 Day 1 is defined as the first day of acalabrutinib administration, and should occur within 30 days of consent. The cycle day count will continue despite a hold in acalabrutinib administration due to toxicities (See [Section 7.2](#)). However, the next cycle will be delayed as long as acalabrutinib is held and will start once acalabrutinib is restarted.

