### **5.10.1 Corticosteroids**

Participants are not permitted to be receiving chronic corticosteroids (>2 weeks within the 4 week period prior to first dose of study medication; at dosages equivalent to prednisone >60 mg/day) at time of screening and enrollment on to this study – see [Section 3.2](#). Concomitant use of corticosteroids for management of AIHA in conjunction with study drug is permitted at this dose, but it is anticipated that a taper will occur while patient is receiving acalabrutinib, and should be completed by the end of 8 weeks on study to a dose of ≤20 mg/day of prednisone or equivalent. The use of corticosteroids for treating AIHA should be in accordance with institutional standards.

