
a. Ideally the clinic visit and all the study requirements should be performed on Day 1 of each cycle as indicated, but may be performed within 7 days before or after the scheduled day. Each treatment cycle is 28 days
 
b. Screening activities to occur within 30 days prior to the start of protocol therapy.
 
c. Protocol therapy may last up to 12 cycles, until unacceptable toxicity or disease progression (see Section 5.6 for more comprehensive list). At the end of 12 cycles, treatment with acalabrutinib may be continued if the study participant might benefit from the ongoing therapy in the opinion of the treating physician.
 
d. An End of Treatment (EOT) visit is required for safety assessments for any subjects who permanently discontinue study drug for any reason, including disease progression. This visit should occur at 30 (<math>\pm 7</math>) days from time of the last dose of study drug to monitor for resolution or progression of AEs and to document the occurrence of any new events, regardless of whether the subject receives a new CLL therapy or demonstrates disease progression within this timeframe. Subjects who withdraw consent for study treatment should still be encouraged to complete the EOT assessments, but these assessments cannot be mandated if subject consent for further study participation is withdrawn.
 
e. Follow-up assessments are to occur in accordance with standard of care, with participants visits occurring at least every 4 months, up to 12 months from time last dose of study drug.
 
f. Informed consent process to be fully documented (see Section 17.4). Informed consent must occur prior to any research only (non-SOC) screening procedures.
 
g. A medical history will be obtained by the investigator or qualified designee. To include information on demographics, all active conditions, and any condition diagnosed within the prior 10 years that are considered to be clinically significant by the Investigator. Details regarding the participant's cancer will be recorded separately and not listed as medical history.
 
h. Eligibility criteria are detailed in Section 3.0.
 
i. Registration into a COH clinical trial management system (CTMS)
 
j. Document the following disease-specific information: number of prior treatment regimens for CLL and AIHA; drugs previously used in the therapy of CLL and AIHA; including (if available): therapy dates, and response, concomitant autoimmune disorders, including hematologic (immune thrombocytopenia, immune-mediated neutropenia) and non-hematologic (e.g., rheumatoid arthritis and other rheumatologic conditions; inflammatory bowel disease [Crohn's disease, ulcerative colitis]), History of ibrutinib intolerance (present versus not), Rai stage at diagnosis (if known) and the time of study entry.
 
k. Current list of medications will be acquired concurrent with medical history. See Section 5.9 for concomitant medication restrictions and guidelines. Baseline transfusion requirements must be assessed prior to start of study drug. Transfusion requirements prior to study start up to 6 months will be collected/documents, if available. Transfusion requirement will be assessed on day 1 of each cycle and number of units of PRBCs and platelets transfused during the previous cycle will be documented. Enter new medications started during the trial through the end of treatment visit. Record all medications taken for grade 3 and 4 SAEs.
 
l. Physical examination must be performed by a medically qualified individual such as a licensed physician, Physician's Assistant or advanced Registered Nurse Practitioner as local law permits. Baseline complete physical exam per institutional standards and may include evaluating: weight, general appearance, head, ears, eyes, nose, throat, neck, skin, cardiovascular system, respiratory system, gastrointestinal system, and nervous system. Height is only required as part of screening. Weight should be recorded at each visit. More extensive physical exams will be performed if guided by the development of new symptoms.
 
m. Vital signs: blood pressure, heart rate, temperature, and oxygen saturation by pulse oximetry.
														

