### 12.4.3 Analysis of the Exploratory Endpoint(s)

Flow cytometry will be used to assess T-cell repertoire and evaluate changes associated with acalabrutinib. The distribution of T-cell subtypes distribution will be described by mean, standard deviation (SD), minimal, and maximal values. Comparison of group variables will be assessed using a nonparametric test of independence (e.g., Chi-square test or Fisher's exact test).

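### For patients entering on prednisone above 20 mg/day, the T-cell baseline precedes the anticipated taper and every later sample follows its deadline, so drug effect and steroid reduction cannot be separated

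*Combined protocol and SAP*

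**What the plan says.** **Sampling.** Table 9.1.2.1 sets the draws at "C1D1, C4D1, C7D1, C13D1". Section 9.1.1.1 adds: "Peripheral blood will be collected prior to study treatment/procedures at the time points indicated in Table 9.1.2.1". Section 11.3 takes the pre-therapy value as the reference and looks at the percentage of T-cell subsets after 3, 6 and 12 cycles.

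**Steroids.** Section 3.2, item 10, excludes only chronic use "in excess of prednisone 60 mg/day or its equivalent within 4 weeks prior to start of study therapy", and it allows rescue steroids during the trial. Section 5.10.1 says: "Concomitant use of corticosteroids for management of AIHA in conjunction with study drug is permitted at this dose". It continues that "it is anticipated that a taper will occur while patient is receiving acalabrutinib", to be completed by the end of 8 weeks at 20 mg/day or less.

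**Analysis.** Section 12.4.3 says: "Flow cytometry will be used to assess T-cell repertoire and evaluate changes associated with acalabrutinib". It plans means, SDs, minima and maxima, and a test of independence such as chi-square or Fisher. It names no paired comparison, no steroid covariate and no split by steroid use.

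**The concern.** The exploratory objective is the effect of acalabrutinib on T cells, and Section 9.0 also describes the measurements as effects of the drug. In a single-arm study, that attribution rests on nothing else of consequence changing between baseline and follow-up.

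In patients entering above 20 mg/day, the prednisone dose is expected to fall in that same interval. If steroid dose affects the T-cell readouts, a shift could come from the drug, from the steroid reduction or from both. Steroid reduction could also mask a drug effect that runs in the opposite direction. Better sample handling or a better test would not resolve this, because no scheduled draw falls after acalabrutinib starts and before the taper deadline.

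The stake is the interpretation of the correlative study. Section 2.3 reports that a T-cell increase seen with ibrutinib was not seen with acalabrutinib, so an apparent shift here would attract attention.

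**Working it through.** The plan states no figure for the T-cell endpoint. Its only design figure is for the primary endpoint (Section 12.2). With n = 20 and rejection at 10 or more responders, the exact binomial gives a type I error of 0.0480 at a 30% rate and power of 0.8725 at 60%. These match the stated 0.048 and 87%. Nothing below depends on them.

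**Step 1: timing.** Inputs:
- Section 5.2: "The treatment cycle will be 28 days".
- Section 10.0, footnote a: visits "may be performed within 7 days before or after the scheduled day".
- Section 5.10.1: the taper deadline is the end of week 8, which is 8 × 7 = day 56.

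The study day of cycle k, day 1 is 28 × (k − 1) + 1.

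| Draw | Study day | Window | Earliest draw minus day 56 |
|---|---|---|---|
| C4D1 | 28 × 3 + 1 = 85 | 78–92 | 22 days |
| C7D1 | 28 × 6 + 1 = 169 | 162–176 | 106 days |
| C13D1 | 28 × 12 + 1 = 337 | 330–344 | 274 days |

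Treatment holds only move later cycles further out (Section 5.2). All three follow-up draws therefore fall after the deadline, even at the early edge of the window.

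**Step 2: who is affected.** A patient on 60 mg/day at C1D1 who meets the target has lost at least 60 − 20 = 40 mg/day by C4D1. This is the case at the eligibility ceiling for chronic use, not a typical patient. A patient entering at 20 mg/day or less already meets the target, and for a patient on no steroid the taper does not arise.

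**Step 3: can the data separate the two?** Section 5.9.1 asks for the name of an added or changed therapy and the reason for it, and does not mention its dose. Section 10.0, footnote k, asks for a current medication list and new medications. The correlative collection form (Appendix F) has no steroid field and serves one site only. Dose on the day of the draw is therefore not assured.

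**Step 4: illustration on assumed inputs.** Suppose the true drug effect is zero. A fraction f of patients have a steroid-driven shift of d SDs of within-patient change, so the mean bias is f × d. A two-sided 5% paired t-test with n = 20, over 40,000 simulated trials, rejects this often:

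| f | d = 0.5 | d = 0.8 | d = 1.0 |
|---|---|---|---|
| 0 | 5.0% | 5.0% | 4.8% |
| 0.25 | 8.1% | 12.5% | 16.2% |
| 0.50 | 17.5% | 34.7% | 47.9% |
| 0.75 | 34.2% | 67.3% | 83.0% |
| 1.00 | 56.4% | 92.3% | 98.8% |

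Neither f nor d is in the documents, and Section 12.4.3 plans no paired test. The table shows how strongly any answer depends on unknown inputs. It does not estimate an error rate for this trial.

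**The case against.** The strongest reply is that this is an exploratory, uncontrolled correlative study that drives no decision, and that Section 12.4.3 speaks only of association. That is fair, and it sets the weight of the point.

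Several further objections also stand:
- **The affected group may be small.** Cold AIHA is eligible, and Section 2.1.2 calls steroids relatively ineffective there. Section 2.4 admits patients who did not tolerate a steroid.
- **The taper is anticipated, not assured.** With rescue steroids allowed, a later sample is after the deadline but not necessarily after a taper.
- **The effect is undocumented.** Nothing in the documents says how far, or in which direction, a steroid reduction would move these T-cell measures.
- **Some data exist.** Concomitant medications are reviewed at the treatment visits.

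A reader might infer that all T-cell change in this trial is confounded with steroid withdrawal, or that the false-positive rate is known to be inflated. The documents support neither. The stated target is a reduction to 20 mg/day or less, which need not be withdrawal. Patients who enter at or below that dose are not exposed to the anticipated taper. No T-cell test with a set significance level is planned that could have an inflated error rate.

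It is also tempting to rest conclusions on patients whose dose stayed unchanged. Dose change happens after treatment starts and may depend on response. An unchanged-dose group would mix patients never on steroid with patients who could not taper because treatment failed.

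None of this answers the timing. For those who enter above 20 mg/day and do taper, the schedule and the analysis leave the two causes inseparable.

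**Conclusion.** The point holds for patients who enter on prednisone above 20 mg/day. For them, the planned change from baseline cannot distinguish acalabrutinib from steroid dose reduction. The timing follows from the documents alone, with a margin of at least 22 days. That the overlap biases the T-cell results rests on the assumption that steroid dose affects those measures.

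The size of the bias cannot be computed. The span of about 8% to 99% covers an affected share of 25% to 100% and a shift of 0.5 to 1.0 SD. Both ranges are assumed, under a test outside the plan. The primary endpoint's sample size and test are untouched. This is a cheap improvement to an exploratory analysis, not a flaw in the trial's main conclusion.

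**What to change.** 1. **Data.** Record the prednisone-equivalent dose on the day of each correlative sample, at all sites, in the eCRF and on the collection form. The form alone would not be enough, since Appendix F covers one site.
2. **Section 12.4.3, main table.** Report within-patient change separately by steroid use at baseline: none or 20 mg/day or less, versus more than 20 mg/day. This split is fixed before treatment, so response cannot influence it. Doses in the lower group may still change, and the recorded doses will show that.
3. **Section 12.4.3, check.** Show the C4D1 to C7D1 and C4D1 to C13D1 contrasts, which lie wholly after the taper deadline. They describe later change on treatment and do not replace the baseline comparison.
4. **Section 12.4.3, sensitivity only.** Label any analysis that adjusts for on-study dose change as a sensitivity analysis, for the reason given under the objection.
5. **Wording.** State that change in patients who entered on higher-dose steroid is not attributable to acalabrutinib alone.

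The cost is one data field and one split in the exploratory tables. The downside is small subgroups in a trial of 22 participants, so the split results will be descriptive. Steroid management itself is unchanged.

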##### 9.1.1.2 *Labeling of blood samples*

Label tubes with COH protocol #, subject ID (issued by DCC), institution, date and actual time point of collection (e.g. C1D1 for Day 1 of Cycle 1), and if applicable patient initials.

##### 9.1.1.3 *Collection and post-collection guidelines*

Refer to Table 9.1.2.3 for collection and post-collection instructions.

**Table 9.1.2.3 Blood sample collection and post-collection instructions.**

Tube Type	Collection details	Site of collection	Post-collection instructions
Green-top	
1- Blood samples will be collected from an indwelling venous catheter or by venipuncture.
 
2- Invert tubes eight times after collection.
 
3- Immediately place the tubes on ice.
	COH Only	
Promptly deliver the blood samples for processing within 4 hours to:
 
[name] Laboratory                  [name]                  City of Hope National Medical Center                  [name], Duarte, CA.

		OSU Site Only	
Promptly deliver the blood samples for processing within 4 hours to:
 
[name] Laboratory                  Ohio State University                  [name]                  Columbus, OH

		MDACC Site Only	
Ship whole blood samples on day of collection overnight at room temp to:
 
[name] Laboratory                  [name]                  City of Hope National Medical Center                  [name], Duarte, CA 91010.
 
Please refer to Appendix F and Appendix G

Peripheral blood mononuclear cells (PBMCs) and plasma will be separated by density gradient centrifugation. Cells will be frozen and stored in liquid nitrogen. Plasma will be stored at -70°C.

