## 9.2 Laboratory Studies Performed

Flow cytometry will be used to evaluate leukocyte subpopulations (e.g., CD3, CD4, CD45, TCRγδ, CD14, CD16, CD56). Additional surface markers will be used to discriminate different maturation stages of effector cells (CD28, CD27, CD45RA, CD3, CD8, CCR7, CD4, CD45): naive T cells, central memory, effector memory and CD45RA expressing effector memory cells; Tregs (CD4+CD25+FoxP3+CD127low); Th17 (IL-17positive). To assess activation levels of circulating T-cells, a panel of activation markers will be used (e.g., CD38, CD25, CD69, HLA-DR). The immunology panel may be expanded to include other markers. Plasma cytokine levels will be measured by ELISA.

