## **APPENDIX G: BLOOD SHIPPING GUIDELINES TO CITY OF HOPE**

---

*These guidelines apply to **MDACC site** only.*

*All biological material must be shipped according to applicable government and International Air Transport Association (IATA) regulations.*

*Shipping guidelines can also be found on the [FedEx website](#).*

1. Aim to ship samples on a **Monday through Thursday**. If this is not feasible, advance arrangements should be made with [name] lab ([[contact]](mailto:[contact])) or designee.
1. Blood samples in green-top tubes will be sent overnight at around 25°C in an appropriate container via FedEx.
2. On the day of shipment, email [name] lab ([[contact]](mailto:[contact])) or designee the FedEx shipment tracking#.
3. Ship samples with a copy of the correlative blood collection form (Appendix F) and a copy of the latest CBC results (with differential) and the date of the test to:

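### Correlative blood follows two handling routes (delivered for processing within 4 hours at COH and OSU, shipped overnight at about 25°C from MDACC) and Section 12.4.3 has no term for route, so exploratory T-cell results may partly reflect handling

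*Combined protocol and SAP*

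**What the plan says.** **Handling.** Table 9.1.2.3 tells COH and OSU to "deliver the blood samples for processing" within 4 hours, each to its own laboratory. The MDACC row has whole blood shipped "on day of collection overnight at room temp to" the COH laboratory. Appendix G, which covers MDACC alone, gives the temperature: "Blood samples in green-top tubes will be sent overnight at around 25°C in an appropriate container via FedEx".

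**Ice.** The collection-details column has one entry, not tied to any site. It says to "place the tubes on" ice immediately.

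**Separation.** The text under the table says "Peripheral blood mononuclear cells (PBMCs) and plasma will be separated by density gradient centrifugation". For MDACC this can happen only after transit.

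**Readouts.** Section 9.2 plans flow-cytometry subsets and activation markers (CD38, CD25, CD69 and HLA-DR are the examples given). It adds: "Plasma cytokine levels will be measured by ELISA". The endpoint in Section 11.3 is subset percentages only, at baseline and after 3, 6 and 12 cycles.

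**Analysis.** Section 12.2.1 defines one exploratory population: eligible treated participants with one or more correlative specimens. Section 12.4.3 says "The distribution of T-cell subtypes distribution will be described by mean, standard deviation (SD), minimal, and maximal values". It then plans a test of independence, with chi-square and Fisher's exact as examples. It mentions no site, route or pairing, and no activation marker or cytokine.

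**Sites.** The synopsis lists COH and OSU as participating sites. MDACC is not listed, but it has its own row in Table 9.1.2.3 and its own Appendices F and G.

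**The concern.** Time and temperature before separation differ by site. The ice step and the 4-hour limit suggest that the authors regard both as relevant to these samples. The planned readouts include activation markers and plasma cytokines, and Section 2.3 gives T-cell activation before and during treatment as the purpose of the correlative work. Section 9.2 also uses CD25 to define regulatory T cells, so the named subset endpoint is not clearly separate from the activation panel.

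Applied as written, the plan gives one set of summary statistics over all participants and an unpaired comparison. Route is then confounded with site in every level. If the proportion of shipped samples differs between C1D1, C4D1, C7D1 and C13D1, a handling difference can look like a change over time on acalabrutinib. If collection and processing times are not recorded at the time, it may be impossible to separate the two later.

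**Working it through.** The plan states no figure on this point, so there is none to reproduce. The check has three steps.

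**1. The two routes side by side**

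| | COH, OSU | MDACC |
|---|---|---|
| After the draw | Ice (shared column) | Ice (shared column) |
| Then | Delivered for processing within 4 hours | Whole blood shipped overnight, about 25°C |
| Term in Section 12.4.3 | None | None |

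Read literally, MDACC tubes go on ice and then travel at room temperature. The two steps might be meant as a sequence, but the table does not say so.

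**2. Effect on levels (illustration only)**

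Let *m* be MDACC's share of participants and *d* the handling shift in within-route SD units. Neither is in the documents. I assume 2 to 11 of the planned 22 participants from MDACC, and *d* from 0.25 to 1.0.

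- Shift in the overall mean = *m·d*
- SD ratio = √(1 + *m*(1−*m*)*d*²)
- Share of variance due to route = *m*(1−*m*)*d*² / (1 + *m*(1−*m*)*d*²)

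| MDACC patients | *d* | Mean shift (SD) | SD ratio | Variance share |
|---|---|---|---|---|
| 2 of 22 | 0.25 | 0.023 | 1.003 | 0.5% |
| 7 of 22 | 0.5 | 0.159 | 1.027 | 5.1% |
| 7 of 22 | 1.0 | 0.318 | 1.103 | 17.8% |
| 11 of 22 | 1.0 | 0.500 | 1.118 | 20% |

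If MDACC enrols nobody, *m* = 0 and every effect is zero.

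**3. Effect on change over visits**

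*Unpaired.* If MDACC's share moves from *m*₁ to *m*₂, the spurious change in the mean is (*m*₂ − *m*₁)·*d*.

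| Share, early to late | *d* = 0.25 | *d* = 1.0 |
|---|---|---|
| 7/22 to 7/15 | +0.037 | +0.148 |
| 7/22 to 4/15 | −0.013 | −0.052 |
| 7/22 to 3/15 | −0.030 | −0.118 |

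For the first row: 0.467 − 0.318 = 0.148, or about 0.15 SD at *d* = 1. It needs all 7 MDACC patients to stay and 7 of the 15 others to leave. If both routes lose patients in proportion, the change is zero.

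*Paired.* With a constant shift, (Y_visit + *d*) − (Y_C1D1 + *d*) = Y_visit − Y_C1D1. The route effect cancels, provided the patient stays at one site and transit affects each sample alike. Section 12.4.3 does not specify this analysis.

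**The case against.** The case against is strong on several points, and most of it stands.

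- **Pooling and proof of bias.** A reader might infer that the plan orders pooling and that the results will measure handling. Section 12.4.3 is silent on site, and no passage gives the size of a handling effect. The documents support only this: one population, one summary and no route term, so handling *may* contribute.
- **Ice at two sites only.** The table could be read as icing COH and OSU blood alone. The ice step is a shared entry, so the finding is a conflict within the MDACC instructions.
- **Diluted within-patient effects.** A reader might infer that shipping blurs each patient's own change. Each site has one route, so a constant effect cancels. Dilution would need transit effects that vary from sample to sample, and the documents do not show that.
- **Cytokines and activation markers.** Section 12.4.3 cannot be said to mishandle these, because it writes no analysis for them. That is a related gap.
- **Excluding shipped samples.** It is tempting to keep shipped blood for subset percentages only and to require separation within 4 hours elsewhere. No passage says that subset percentages are stable overnight, and CD25 serves both panels. The 4-hour rule governs delivery for processing and is not clearly a separation deadline. Appendix F, which records a clock time of collection, is headed for MDACC only.
- **Scope.** If MDACC does not enrol, only an editorial inconsistency remains.

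What survives is that the plan does not specify the paired analysis that would protect the comparison. Nor does it say how shipped samples are treated.

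**Conclusion.** The point holds as a small, inexpensive improvement to the exploratory objective. The difference in handling, the conflicting temperature instructions and the mismatch in site lists are on the face of the documents. That results may partly reflect handling is a reasonable risk, not a demonstrated bias.

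Under the assumed ranges, route could account for 0.5% to 20% of the variance in levels. With the site-mix shifts shown, the spurious change over visits is at most about 0.15 SD in either direction. These figures depend entirely on assumed values for MDACC's share, the handling shift and differential loss to follow-up. The primary endpoint is clinical AIHA response and uses none of these samples, so it is unaffected.

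**What to change.** 1. **Section 12.4.3.** Analyse subset percentages, activation markers and plasma cytokines as paired within-patient changes from C1D1. Summarise them by processing route (local versus overnight-shipped), and add a sensitivity analysis that omits shipped samples. Mandatory exclusion is not needed.
2. **Data capture.** Record clock times of collection and of the start of processing at all sites. Section 9.1.1.2 asks for the date and a visit label such as C1D1, which is not clearly a clock time.
3. **Table 9.1.2.3 and Appendix G.** Reconcile the ice and room-temperature instructions for MDACC.
4. **Site list.** Reconcile the synopsis with the MDACC row and Appendices F and G. If MDACC is not a site, remove them. The route analysis then becomes unnecessary.

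The cost is two time fields, some wording and a little more analysis. The drawback is small numbers within each route, so the by-route summaries would be descriptive.
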